## 8. STUDY DESIGN

[figure not shown]
## 8.1 Summary of Study Design

This will be a multi-centre randomised control superiority trial. Participants will be randomised to either standard colonoscopy (control arm) or colonoscopy plus WISE VISION® CAD device (intervention arm). The CAD device has both detection and characterisation functions and there are 2 elements within the study. Firstly the study will aim to assess the impact of computer aided detection and secondly computer aided characterisation.

When polyps are identified, these will be recorded and the endoscopist will be required to assess this and indicate their optical diagnosis accordingly. For patients randomised to colonoscopy plus CAD, the CADx will then be carried out and the results recorded. Polyps will be treated according to standard care.

Polyps detected by the endoscopists but missed by the CADe device will also be recorded. The total number of polyps identified and the endoscopist diagnosis will be recorded for both arms. The histology results of the polyps removed will be collected.

Figure 1: Study Procedure Flowchart

## 8.2 Primary and Secondary Endpoints/Outcome Measures

## **Primary End points**

Adenoma detection rate in both arms PIVI-2: NPV of adenoma diagnosis in diminutive (<5mm) recto-sigmoid polyps in both arms

## Secondary End points

COLOVISION Protocol v1.0 18/08/2022 IRAS ID: 313559 Polyp detection rate (PDR) in both groups

Adenoma per colon (APC) in both groups

PIVI-1: agreement between surveillance interval decisions based on histology and that based on the combination of histology of non-diminutive polyps and optical diagnosis in both arms

Diagnostic performance measures in both groups (sensitivity, specificity, accuracy, NPV, PPV, AUC)

Diagnostic performance measures in both groups (sensitivity, specificity, accuracy, NPV, PPV, AUC) according to endoscopists experience

Diagnostic performance measures in both groups (sensitivity, specificity, accuracy, NPV, PPV, AUC) according to endoscopy imaging mode (WLI or EI)

The proportion of histological assessments that could have been avoided in both arms

The proportion of polyp removals that could have been avoided in both arms

Withdrawal time in both groups

# 9. STUDY PARTICIPANTS

### 9.1 Study Setting

This will be an international multi-centre trial being carried out at several secondary care endoscopy sites across Europe. All endoscopists working on the study at participating sites will have access to and be trained in the use of WISE VISION® device.

The trial will run at the following sites:

- Queen Alexandra Hospital, Portsmouth, UK (Sponsor & lead UK site)
- Royal Sussex County Hospital, UK
- St Georges Hospital, UK
- King's College Hospital, UK
- Humanitas Research Hospital, Milan, Italy
- GastroZentrum Lippe, University Medical Centre Mainz, Germany
- Sapienza University of Rome, Italy

## 9.2 Overall Description of Study Participants

All patients who are undergoing a colonoscopy at one of the participating sites will be screened, and those who meet eligibility criteria below will be invited to participate.

## 9.3 Eligibility Criteria

Inclusion

• Adults over age 18 who are undergoing a colonoscopy

• Must be able to give informed consent

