## Exclusion

- Pregnant patients
- Poor bowel preparation
- Polyposis syndrome
- Active inflammation of the colon including inflammatory bowel disease
- Incomplete colonoscopy

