## 10. SAMPLING

- This is powered as a superiority trial.
- For computer aided detection, the ADR of competent but non-expert endoscopists is assumed to be 20% and we believe that CADe will increase it to 30% (expert level). In order to demonstrate a difference of 10% between the two groups with an 80% power and a significance level (alpha) 0.05; we will need 588 patients (294 per group). We will over recruit by 10% (max total of 654) to allow for drop outs, poor bowel prep, incomplete dataset etc. Interim analysis will be done after 50% recruitment
- For computer aided diagnosis, the NPV of endoscopists is assumed to be 75%, and we believe the NPV of endoscopist plus CADx will be 90%. To achieve this with an 80% power and significance level (alpha) of 0.05, we will need to assess 200 diminutive recto-sigmoid (100 per group) polyps (588 total polyps), in an estimated 168 patients. We will plan to over recruit by 10% to allow for incomplete data (220 diminutive recto-sigmoid polyps, 647 total polyps). Interim analysis will be done after 50% recruitment

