### 11.3 Randomisation

Participants will be randomised electronically in a 1:1 ratio into two groups. The intervention group will have their colonoscopy performed with the assistance of the WISE VISION® CAD system, the control arm will have standard colonoscopy. Randomisation will be carried out prior to the procedure being started. The randomisation will be stratified by site to ensure an equal allocation in each centre. Additionally, a blocked randomisation, with varying block sizes, will be performed to allow for a balance between groups throughout the trial.

The randomisation process will be managed using the built-in module within the project's REDCap eCRF database managed by Portsmouth Hospitals University NHS Trust. The Data Manager will generate the randomisation allocation table using statistical software, which will then be uploaded into REDCap before the first patient is consented.

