## 11.4 Study Assessments

Baseline characteristics will be recorded for all participants. Basic demographics will be recorded to include:

- Age
- Sex
- Co-morbidities and ASA score
- History of previous polyps/bowel conditions

During the colonoscopy the following will be recorded in all patients:

- Endoscopist including level of experience (number of life time procedures)
- Indication
- Bowel preparation used and quality
- Use of sedation/general anaesthetic
- Procedure start and finish time and time of maximal intubation
- Comfort score
- Adverse events
- Polyps detected to include the endoscopists optical diagnosis and assessment of size, morphology using the Paris classification, site and details of their removal.
- Still image/video of polyp (where available)

For patients randomised to colonoscopy plus CAD the following additional data will be recorded:

- Total number of potential polyps identified by CADe
- CADx diagnosis of polyps identified
- Outcome of assessment by endoscopist e.g. confirmed as polyp, characterisation assessment

Post colonoscopy:

- Adverse events will be recorded
- Histology of any polyps removed will be recorded to correlate with the endoscopist/CADx assessment of the lesion.

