#### 14.2 Analysis of Endpoints

The primary outcome, ADR, will be compared between groups using the Chi-square test. The difference in the proportion of patients with an adenoma detected between groups will be quantified, along with a corresponding 95% confidence interval.

Within both groups, a descriptive analysis of percentage of polyps correctly identified, relative to the histological diagnosis, will be reported.

For all detection outcomes, a series of sensitivity analyses will be performed, repeating the analyses, but this time only considering polyps in the CAD intervention group if they were correctly identified based on their histology.

Binary secondary outcomes will be analysed using the Chi-square test. Continuous secondary outcomes will be compared between groups using the unpaired t-test, if found to be normally distributed, or the Mann-Whitney test otherwise.

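### Section 9.3 admits patients booked for a lesion that is already known, and they would dilute the ADR difference by an amount the protocol leaves open

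*Protocol*

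**What the plan says.** Section 9.2 sets an all-comer population: "All patients who are undergoing a colonoscopy at one of the participating sites will be screened". Section 9.3 then requires "Adults over age 18 who are undergoing a colonoscopy" and the ability to give informed consent. The exclusions are pregnancy, poor bowel preparation, polyposis syndrome, active colonic inflammation and incomplete colonoscopy. The nearest to the present point is "Polyposis syndrome", which concerns a syndrome and not a single polyp seen at an earlier examination.

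Section 11.4 collects the indication and "History of previous polyps/bowel conditions", so a mix of indications is foreseen. Neither item affects eligibility or allocation: "The randomisation will be stratified by site to ensure an equal allocation in each centre" is the only stratification described in 11.3.

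The first primary endpoint in 8.2 is "Adenoma detection rate in both arms". Section 14.2 compares it by a chi-square test and adds: "The difference in the proportion of patients with an adenoma detected between groups will be quantified". Section 14.1 makes the analysis intention to treat. Neither 8.2 nor 14.2 distinguishes an adenoma known before the procedure from one found during it.

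Section 10 plans on an ADR of 20% rising to 30%: "In order to demonstrate a difference of 10% between the two groups with an 80% power", alpha 0.05, 294 patients per group, with recruitment up to 654.

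**The concern.** The first primary objective (7.1) is the effect of the system on endoscopists' detection of polyps. When a patient is sent for removal of a lesion already described elsewhere, the endoscopist knows that it exists and roughly where it is. If the lesion is an adenoma, the patient's binary ADR outcome is largely settled before randomisation and is the same in both arms.

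Each such patient takes a place in the sample and adds almost nothing to the between-arm contrast in ADR. Two things follow. The absolute difference shrinks in proportion to the share of these patients, and both proportions move towards 50%, where the binomial variance is larger. Both reduce the chance of showing a real detection effect.

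**Working it through.** **Inputs from the protocol (section 10).** p1 = 0.20, p2 = 0.30, alpha 0.05 (taken as two-sided, which reproduces the stated size), power 80%, n = 294 per group, maximum total 654.

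**Assumptions, not in the protocol.** f is the share of enrolled patients with a known lesion. y is the proportion of those patients who count as having an adenoma in either arm, set at 0.90 and varied below. All other patients follow 20% versus 30%.

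**Step 1: reproduce the plan.** With pooled variance under the null and no continuity correction,

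n = [1.960 × √(2 × 0.25 × 0.75) + 0.842 × √(0.20 × 0.80 + 0.30 × 0.70)]² / 0.10² = (1.2003 + 0.5119)² / 0.01 ≈ 293.2, so 294 per group and 588 in total.

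588 / 0.9 = 653.3, so 654. Both stated figures reproduce.

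**Step 2: dilution.** With a share f of known-lesion patients,

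p1(f) = f·y + (1 − f) × 0.20 and p2(f) = f·y + (1 − f) × 0.30,

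so the difference is 0.10 × (1 − f), whatever the value of y.

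**Step 3: power.** With p̄ the mean of p1 and p2,

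power = Φ{ [(p2 − p1)√n − 1.960 √(2p̄(1 − p̄))] / √(p1(1 − p1) + p2(1 − p2)) }.

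Example, f = 10%: p1 = 0.27, p2 = 0.36, p̄ = 0.315. The argument is (0.09 × √294 − 1.960 × 0.6569) / 0.6538 = (1.5432 − 1.2875) / 0.6538 = 0.391, and Φ(0.391) = 0.652.

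| f (assumed) | Control ADR | CAD ADR | Difference | Power, 294 per group | Power, 327 per group |
|---|---|---|---|---|---|
| 0% | 20.0% | 30.0% | 10.0 points | 80.1% | 84.1% |
| 1% | 20.7% | 30.6% | 9.9 points | 78.6% | 82.8% |
| 2% | 21.4% | 31.2% | 9.8 points | 77.1% | 81.4% |
| 5% | 23.5% | 33.0% | 9.5 points | 72.6% | 77.1% |
| 10% | 27.0% | 36.0% | 9.0 points | 65.2% | 69.8% |
| 20% | 34.0% | 42.0% | 8.0 points | 51.5% | 55.9% |

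The last column takes all 654 as evaluable. It is an upper bound, because section 10 sets that margin aside for drop-outs, poor preparation and incomplete data.

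**Step 4: sensitivity to y.** At 294 per group and f = 5%, 10% and 20%, power is 72%, 64% and 51% if every known lesion counts (y = 1), 73%, 66% and 52% at y = 0.80, and 75%, 69% and 56% at y = 0.50. The result is driven by f and depends little on y.

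**The case against.** Several points on the other side stand.

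- **The planning rates may already be all-comer rates.** A reader might infer that the stated 80% power is wrong for the population in 9.3. The protocol does not support that. Section 10 gives 20% as the ADR of competent non-expert endoscopists, and section 5 cites 20% as a general performance target. Neither says that adenomas known beforehand are left out. If 20% and 30% are meant for everyone 9.3 admits, power is 80% by construction.
- **The share is unknown and may be small.** Nothing in the protocol indicates that f reaches 10% or 20%. At 1% or 2% the loss is one to three percentage points, and full evaluability of the 654 would more than cover it.
- **This is not bias towards an arm.** A reader might call the result biased towards no effect. Allocation is 1:1 and stratified by site, so these patients are expected equally in both arms. The risk difference remains a valid estimate for the population enrolled. What is lost is contrast and power.
- **Optical diagnosis.** A reader might extend the point to the NPV and PIVI-1 endpoints, on the ground that an earlier report could inform the endoscopist. No figure in the protocol shows that known lesions form a meaningful part of the diminutive rectosigmoid polyps. In PIVI-1 the non-diminutive polyps enter through histology. The point is limited to ADR.
- **All-comer recruitment is a coherent pragmatic choice,** and these patients can still contribute additional adenomas to the adenoma-per-colon endpoint.

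It can also be said that a statistical analysis plan might define a detected adenoma more narrowly. It might, but eligibility is fixed in the protocol. An analysis that dropped these patients later would use up sample size that section 10 does not allow for. Excluding them would still leave screening, surveillance and symptomatic patients eligible.

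**Conclusion.** The point holds as a gap in eligibility. Section 9.3 lets in patients booked for a known lesion, and nothing in the ADR endpoint or its analysis as written sets that lesion aside. Such patients dilute the ADR difference by the factor (1 − f) and lower power, without favouring either arm.

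The mechanism is certain; its size is not. It rests on the assumed f, on an assumed 90% adenoma yield, and on reading 20% versus 30% as the rates in all other patients. On those terms the loss is slight at 1% to 2%, about 7 points of power at 5% (80.1% to 72.6%) and about 15 points at 10% (80.1% to 65.2%). This is a cheap improvement, not an error in the sample size calculation.

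**What to change.** Add one line to the exclusions in 9.3: *Colonoscopy booked for removal, re-inspection or site check of a polyp or lesion already identified at an earlier examination or imaging.* It can be checked from the referral during the pre-procedure screening in 11.1.

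If such patients have already been enrolled, pre-specify a sensitivity analysis of ADR that leaves them out by indication. Section 11.4 already records the indication, although it lists it among the items recorded during the colonoscopy. The value should be taken from the referral, so that it cannot depend on the arm or on what is found.

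The cost is a slightly smaller pool of eligible patients. No additional data item is needed, provided the recorded indication identifies a booking for a known lesion.

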## Exclusion

- Pregnant patients
- Poor bowel preparation
- Polyposis syndrome
- Active inflammation of the colon including inflammatory bowel disease
- Incomplete colonoscopy

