## 11.5 Discontinuation/Withdrawal of Participants from Study Treatment

Participants are free to withdraw their consent at any point during the study if they wish. Data collected up to the point of withdrawal will still be included in the analysis.

The withdrawal of a participant in the study will also be required in the following situations:

- obstructing lesions
- inability to complete the procedure e.g. difficult colonoscopy

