#### 14. DATA ANALYSIS

## 14.1 Description of Analysis Populations

Analysis will be carried out on an intention to treat basis.

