# 14.3 Procedure for Dealing with Missing, Unused and Spurious Data

We expect very little missing data due to non-response given the nature of the intervention in this study. If the amount of missing data is not significant, we will use listwise deletion (i.e. only subjects with complete data will be included in the full ITT primary analysis). If the amount of missing data is significant, we will use standard statistical/imputation methods to deal with that and minimise data loss.

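### Exclusions that become known only after randomisation conflict with the intention-to-treat analysis and leave the ADR denominator open to a judgement made with the arm known

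*Protocol*

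**What the plan says.** All references are to the protocol.

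- **Section 11.3:** "Randomisation will be carried out prior to the procedure being started".
- **Section 9.3, Exclusion:** lists poor bowel preparation and "Incomplete colonoscopy". It does not say what happens if either is found after allocation.
- **Section 11.5:** withdrawal is mandatory for obstructing lesions and for "inability to complete the procedure e.g. difficult colonoscopy". The same section states: "Data collected up to the point of withdrawal will still be included in the analysis". That sentence directly follows the one on withdrawal of consent.
- **Section 10:** 588 patients are raised to a maximum of 654 "to allow for drop outs, poor bowel prep, incomplete dataset etc".
- **Section 14.1:** "Analysis will be carried out on an intention to treat basis". This is the whole definition of the analysis population.
- **Section 14.3:** if missing data are not significant, "only subjects with complete data will be included in the full ITT primary analysis"; otherwise imputation is foreseen.

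Section 11.3 gives CAD support to one arm only, no blinding is described, and the synopsis leaves decisions during the procedure to the endoscopist. The person judging preparation and completeness therefore knows the arm.

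**The concern.** An eligibility criterion protects a randomised comparison only if it is settled before allocation. Here one criterion cannot be, and another normally is not. If they are applied as listed, whether a randomised patient counts towards ADR depends on a later judgement by someone who knows the arm and may already know what has been found. Section 11.4 records preparation quality, but no cut-off for poor is given.

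Poor preparation or an incomplete examination plausibly lowers the chance of finding an adenoma, although the protocol does not say so. Under that assumption, removing such patients raises the observed ADR in whichever arm loses more of them. The endpoint at stake is a primary one. Two analysts could also build different denominators, each citing the protocol.

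**Working it through.** **Who is in the denominator?**

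| Patient found, after randomisation, to have | Pointing to removal | Pointing to retention |
|---|---|---|
| Poor preparation | 9.3 exclusion; 10 counts it as a loss | 14.1 |
| Incomplete colonoscopy | 9.3 exclusion; 11.5 mandatory withdrawal | 14.1; 11.5 retention sentence, if it reaches this case |
| Obstructing lesion | 11.5 mandatory withdrawal | 14.1; 11.5 retention sentence, if it reaches this case |
| Incomplete data | 14.3, if missing data are not significant | 14.1; 14.3 imputation otherwise |

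No row has a single answer. Removal is best supported for poor preparation: had those patients stayed in the denominator, section 10 would not need to replace them.

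**The plan's own figure.** Inputs from section 10: ADR 20% and 30%, power 80%, alpha 0.05 (taken as two-sided). With p̄ = 0.25,

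n per arm = [1.96·√(2·0.25·0.75) + 0.8416·√(0.20·0.80 + 0.30·0.70)]² / 0.10² = 293.2, so 294 per arm and 588 in all. Then 588/0.9 = 653.3, so 654. Both figures reproduce. The allowance is 654 − 588 = 66 patients.

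**Illustration of bias.** The protocol gives no exclusion rates, so these are assumptions: 327 randomised per arm, true ADR 20% in both arms, and no adenoma in any excluded patient. Observed ADR = 0.20/(1 − fraction excluded).

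| Excluded, CAD vs control | Observed ADR | Difference | Analysed per arm | SE | Chance of p<0.05 |
|---|---|---|---|---|---|
| 10% vs 5% | 22.22% vs 21.05% | +1.17 | 294 vs 311 | 3.35 | 6.4% |
| 10% vs 2% | 22.22% vs 20.41% | +1.81 | 294 vs 320 | 3.30 | 8.5% |
| 10% vs 10% | 22.22% vs 22.22% | 0 | 294 vs 294 | 3.43 | 5.0% |

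Differences and SEs are in percentage points. The last column is 1 − Φ(1.96 − d/SE) + Φ(−1.96 − d/SE), with d the difference. If excluded patients have an ADR of 5% instead of 0%, observed ADR = (0.20 − 0.05·e)/(1 − e), with e the fraction excluded. The first two differences become +0.88 and +1.36 points. Exchanging the arms reverses the sign.

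Equal rates alone are not enough. Suppose 10% are excluded in each arm, all without an adenoma under CAD but a random sample of controls. Observed ADR is then 22.2% vs 20.0%, and the chance of p<0.05 is about 10%. This is an extreme case.

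**Power if everyone is kept.** Assume 10% of patients are affected, with 654 randomised.

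- None has an adenoma detected: 0.9·20% = 18% vs 0.9·30% = 27%. The same formula gives 337 per arm, 674 in all; 654 gives 78.8% power.
- They have half the assumed ADR: 0.9·20% + 0.1·10% = 19% vs 0.9·30% + 0.1·15% = 28.5%. The requirement is 314 per arm, 628 in all; 654 gives 81.6% power.

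**The case against.** A reader might infer that all these patients are certainly removed. The protocol does not support that. Section 11.5 concerns withdrawal from study treatment and says data up to withdrawal stay in; with 14.1, one fair reading keeps obstructed and uncompleted cases in their arm. The reach of that sentence is unclear, so the fault there is a contradiction. It does not address the section 9.3 exclusions.

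A reader might also infer that the whole 10% over-recruitment replaces such patients. Section 10 names poor preparation, but neither incomplete colonoscopy nor obstruction.

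Listwise deletion in 14.3 is conditional, and an incomplete procedure is not the same as incomplete data: a poorly prepared patient with no adenoma found has an observed outcome. What stands is that a complete-case set is labelled full ITT when the condition is met.

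Finally, a reader might conclude that ADR will be biased in favour of CAD. Nothing in the protocol establishes arm-specific exclusion rates, selectivity or direction. The link with finding no adenoma is plausible but unsourced, and weakest for obstruction, where the reason for withdrawal may itself be a lesion. Section 11.4 does record preparation quality and time of maximal intubation for everyone, so reporting by arm is feasible. That helps diagnose the problem but does not settle the primary set.

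Missing-data detail may fairly be left to a statistical analysis plan. The conflict between exclusion, withdrawal and ITT is in the protocol's own text.

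**Conclusion.** The point holds as an inconsistency that leaves a primary endpoint open to bias. It is firmest for poor preparation and incomplete colonoscopy: randomisation comes first, the exclusions follow, and ITT is still claimed. For obstructing lesions and uncompleted procedures, the patients' status is contradictory.

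Under the assumed rates the spurious ADR difference is 1.2 to 1.8 points, or 12% to 18% of the 10-point target, with a false-positive rate of about 6% to 9%. These figures show scale only. They rest on exclusion that differs by arm and falls on patients without an adenoma; with equal and equally selective exclusion there is no bias under no effect. That no one is blinded to the arm during the procedure is inferred from the design. The sample size arithmetic is correct.

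**What to change.** Reconcile sections 9.3, 10, 11.5, 14.1 and 14.3 on who is analysed. This concerns the analysis set only, not the conduct of the procedure.

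1. State that poor preparation or an incomplete colonoscopy found after randomisation does not remove a patient from the primary ADR analysis, and say whether the retention sentence in 11.5 covers the mandatory withdrawals.
2. Define the primary ADR set as all randomised patients, analysed as allocated, with no adenoma found counted as not detected whatever the preparation or completeness. If it is limited to patients whose colonoscopy was started, call it modified ITT and report the others by arm.
3. Do not label a complete-case set as ITT.
4. Report the set without poor preparation and incomplete procedures as a sensitivity analysis, with numbers and reasons by arm.

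The cost is protocol wording and some dilution of ADR and of the difference. In the less favourable 10% scenario the difference falls from 10 to 9 points, and 80% power would need 674 patients, 20 above the stated maximum. State the expected power, about 78.8% to 81.6% under these assumptions, next to the sample size.
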